This study is a multicenter randomized trial comparing per oral pancreatoscopy-guided lithotripsy (**PPL**) using either laser lithotripsy (**LL**) or electrohydraulic lithotripsy (**EHL**) with extracorporeal shock wave lithotripsy (**ESWL**) in removing main pancreatic duct (**PD**) stones from patients with chronic calcific pancreatitis. Specific aims for this trial include:

- **SA1:** To determine whether PPL is more effective than ESWL in removing PD stones in terms of main pancreatic duct stone clearance rate in patients with chronic calcific pancreatitis.
- **SA2:** Evaluate the effectiveness of main pancreatic duct stone removal in reducing pain and improving quality of life in patients with chronic calcific pancreatitis.
 - **SA2a:** To determine whether a greater clearance of PD stones via PPL or ESWL will improve quality of life to a greater extent.
 - **SA2b:** To determine whether a greater clearance of PD stones via PPL or ESWL will reduce pain and opiate requirements to a larger extent.

The primary endpoint of this trial will be complete clearance of main PD stones in eligible patients. This study will be statistically powered to detect superiority of PPL over ESWL in this primary endpoint. Major secondary endpoints will include: 1) change in quality of life after PD stone removal; 2) change in pain levels after PD stone removal; 3) change in opiate use after PD stone removal; 4) comparison of total number of procedures in both arms, and 5) PD stone recurrence rate.

3. Sample and Methodology

We will enroll 150 subjects (**Figure 1**) with chronic pancreatitis who have symptomatic main PD stones identified by non-invasive imaging, endoscopic ultrasound or prior endoscopic retrograde pancreatography (**ERP**).

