Following baseline assessments and identification of main PD stones, patients will be randomly assigned to receive either PPL or ESWL as the primary lithotripsy method to fracture PD stones. Both these procedures represent potential next steps in the algorithm of managing PD stones.³ If partial clearance (removal of some, but not all stones) of PD stones is achieved as determined by the performing endoscopist, subjects can receive repeated PPL or ESWL sessions (for a maximum of 4 sessions total as is commonly practiced before referral for alternative therapy) until complete removal of stones is achieved.⁵ Failure to remove any main PD stones will be considered a failure of the treatment. Additionally, failure to achieve complete clearance within a maximum of 4 sessions of either PPL or ESWL will be considered a treatment failure, even if partial clearance is achieved.

Cross-over and/or combination therapy will be allowed at the discretion of the endoscopist after treatment failure. As described in the statistical analysis, under the intention-to-treat (primary) analysis, should cross-over occur, the final outcome of complete stone clearance will be attributed to the initial therapy. Under the per-protocol (secondary) analysis, in the case of cross-over, the final outcome of complete stone clearance will be attributed to the combination of ESWL and PPL. Similarly, in terms of survey collection, should cross-over occur, the analysis of the survey results will be attributed to the

originally assigned intervention in the intention-to-treat (primary) analysis. In the per-protocol (secondary) analysis, the outcomes will be attributed to the combination of both interventions resulting in technical success.

Patients who are randomized and subsequently found to have an exclusion criteria identified will continue follow-up per study protocol.

Stone clearance will be determined by occlusion pancreatography showing the absence of main PD stones. Complete stone clearance will be defined as the absence of stones in the head or body of the main PD. Partial stone clearance will be defined as the removal of more than 50% but less than 100% of stone/stone fragments in the head or body of the main PD.

[figure not shown]
Recurrence will be defined as the presence of stones following confirmed clearance in the final pancreatogram. To be considered as recurring, the stone must require intraductal lithotripsy for removal.

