Following complete PD stone removal, patients will be given a validated quality-of-life instrument, the PANQOL¹⁸, at 1, 3, 6, 12, 18, and 24 months post-treatment. Similarly, the visual analog scale will also be given at 1, 3, 6, 12, 18, and 24 months post-treatment. Lastly, daily opiate use will be recorded at 1, 3, 6, 12, 18, and 24 months post-treatment. The 1, 3, 6, 12, 18, and 24-month assessments will have a ± 2 weeks window to be completed.

In order to ensure that subjects respond to the questionnaires as required, REDCap will be programmed to automatically send three reminders to the participants' email when the questionnaires are due. Furthermore, the study coordinator will make three separate attempts to contact non-responding patients within the designated timeframe. If a patient remains unresponsive, these instances will be documented as protocol deviations.

Documentation on interventions for chronic pancreatitis occurring outside of scheduled appointments will be recorded a separate CRF ("non-scheduled chronic pancreatitis interventions"). This CRF will encompass any pancreatic interventions (other than POP x ESWL planned visits) taking place between the subject's consent form signature and their final follow-up.

All patients will have a HgbA1c and fecal elastase drawn at baseline (within 12 months prior to treatment initiation) and at the 1-year mark from treatment completion. Laboratory tests will be drawn per standard of care, and tests results will be added to the REDCap database.

Figure 1: Study Flowsheet

4. Subject Inclusion and Exclusion Criteria

4.1 *Inclusion Criteria:*

1. Subjects aged 18-89
2. Subjects with abdominal pain secondary to chronic calcific pancreatitis and main pancreatic duct stones found on cross-sectional imaging, EUS, or ERP with upstream PD dilation
3. Main PD stones in the head or body that are greater than 50% in size of the immediate downstream diameter of the pancreatic duct
4. Stones ≥ 5 mm in diameter or impacted in the main PD on cross-sectional imaging or EUS

4.2 *Exclusion Criteria:*

1. Subjects who have previously received PPL or ESWL for PD stones within 12 months of enrollment
2. Patients with PD stones isolated in the tail or side branches of the main duct
3. Pancreatic tail stones comprising more than one-third of the stone burden within the main PD, if multiple locations of stones are noted within the main PD
4. Nontraversable ansa loop with upstream stones

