Statistical Analysis: Comparison of technical success rate, defined as the rate of complete clearance of PD stones, between PPL and ESWL will be performing using the chi-squared test or Fisher's exact test. Secondary outcomes including adverse event (both overall and serious adverse event) rates, procedure length, and number of procedures will be compared using a chi-square test or Fisher's exact test for categorical variables and the Student's t test will for continuous variables. A p value <0.05 will be considered significant. In the primary analysis, all results will be analyzed under an intention-to-treat protocol. A per-protocol (secondary) analysis will also be performed where the technical success will be attributed to the combination of modalities resulting in achieving the primary outcome should cross-over occur.

To identify predictors for technical success, a multivariable logistic regression will be performed incorporating variables that were associated ($p<0.2$) with technical success on univariate analysis.

In terms of secondary outcomes, change in PANQOLI scores, VAS scores, and opiate daily doses will be compared between subjects in the PPL group and ESWL group. Additional outcomes to be measured include stone recurrences and number of chronic pancreatitis-related hospitalizations during the follow-up period. Should cross- over occur, under the primary (intention-to-treat) analysis, the outcomes will be attributed to the initially randomized intervention. In the secondary (per-protocol) analysis, the outcomes will be attributed to the combination of treatments resulting in technical success. A subgroup analysis will also be performed on patients who achieved only partial stone clearance (thus considered a treatment

failure) in the above-mentioned outcomes. Comparisons will be made using a chi-squared test or Fisher's exact test for categorical variables and the Student's t test for continuous variables. Paired t tests will be performed to evaluate individual changes within each arm. A p value <0.05 will be considered significant.

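### Stone recurrence is defined without a location limit and tested as a crude proportion, so it can count tail stones never removed, depends on length of follow-up, and is not a randomised comparison

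*Combined protocol and SAP*

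**What the plan says.** Section 2 (Basic Design of the Study) lists recurrence last among the major secondary endpoints: "5) PD stone recurrence rate". The synopsis does not list it.

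Section 3 (Sample and Methodology) defines it: "Recurrence will be defined as the presence of stones following confirmed clearance in the final pancreatogram". A qualifier follows: "To be considered as recurring, the stone must require intraductal lithotripsy for removal". Neither sentence names a duct segment, a time point or a denominator, or requires that the stone be new.

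The same section describes clearance in two ways. One sentence reads "Stone clearance will be determined by occlusion pancreatography showing the absence of main PD stones". The next reads "Complete stone clearance will be defined as the absence of stones in the head or body of the main PD".

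Section 4.2 excludes patients with several stone locations only above a threshold: "Pancreatic tail stones comprising more than one-third of the stone burden within the main PD". A tail share of up to one-third is therefore allowed.

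Section 9 (Data Analysis Plan) says "Additional outcomes to be measured include stone recurrences and number of chronic pancreatitis-related hospitalizations during the follow-up period". Categorical outcomes are compared by chi-squared or Fisher's exact test, under intention to treat first. When a patient crosses over after treatment failure, Section 3 credits the final clearance to the arm first assigned.

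Follow-up runs to 24 months in the synopsis and Section 3, and to 12 months per patient in Section 11. Section 7 stops the study once the sample size is reached and 6-month follow-up has been obtained.

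**The concern.** A recurrence rate should show whether a duct that was cleared stays clear, and whether that differs between techniques. Three features stand in the way.

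1. **Location.** The segments that must be clear (head and body) are narrower than the region in which a recurrence can be counted (not limited). A residual stone can pass as a new one.
2. **Time.** A proportion with recurrence has a meaning only at a stated follow-up length. The documents give three lengths, and the planned test uses none of them.
3. **Who can have the event.** A patient never cleared cannot recur. Restricting to cleared patients conditions on a result of treatment. Counting over all randomised patients scores each uncleared patient as free of recurrence.

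At stake is the reading of one major secondary endpoint, and with it any statement that clearance lasts longer after one technique.

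**Working it through.** **Inputs from the documents.** Clearance of 70% (ESWL) and 90% (PPL), 62 evaluable and 75 enrolled per arm, two-sided 0.05, 80% power (Section 9). The documents give no recurrence rate, so every recurrence figure below is an assumption.

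**The plan's own figure.** n per arm = [1.96·√(2·0.8·0.2) + 0.8416·√(0.7·0.3 + 0.9·0.1)]² / 0.20² = 61.6, so 62 per arm and 124 in total, as stated. 62 × 1.2 = 74.4, so 75 per arm. There is no figure for recurrence to reproduce.

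**1. Tail stones.** Suppose a patient enters with a quarter of the main-duct burden in the tail, which Section 4.2 allows. Head and body are cleared and the tail stone stays. On the head-or-body sentence this is complete clearance. If the tail stone later needs intraductal lithotripsy, stones are present after confirmed clearance and the qualifier is met, so it counts as a recurrence. On the other sentence, which has no tail exception, the same patient was never cleared and cannot recur. The two sentences classify one patient in opposite ways.

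**2. Follow-up length.** Assume a constant hazard and a 24-month risk of 20%.
- 12 months: 1 − 0.8^(12/24) = 10.6%
- 6 months: 1 − 0.8^(6/24) = 5.4%

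The crude proportion changes nearly fourfold with the follow-up statement that applies. If patients are followed for different lengths, it is an average over an unstated mix.

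**3. Denominator.** With 75 per arm, the expected number cleared is 52.5 (ESWL) and 67.5 (PPL). Assume that PPL clears everyone ESWL would clear plus 15 more, that there is no cross-over, and that the 52.5 recur at 20% in both arms. Let the extra 15 recur at rate h.

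| h | Cleared only: ESWL, PPL | All randomised: ESWL, PPL |
|---|---|---|
| 20% | 10.5/52.5 = 20.0%, 13.5/67.5 = 20.0% | 10.5/75 = 14%, 13.5/75 = 18% |
| 40% | 20.0%, 16.5/67.5 = 24.4% | 14%, 16.5/75 = 22% |

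In simulated trials with an uncorrected chi-squared test at two-sided 0.05, PPL was declared significantly worse as follows (nominal 2.5% in that direction):
- h = 20%: about 2.5% of trials (cleared only) and 10% (all randomised).
- h = 40%: about 8% and 25%.

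With cleared patients only, the bias is zero unless the extra patients recur at a different rate. With all randomised patients, the penalty needs no such assumption, only a gap in clearance.

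**4. Cross-over.** Section 3 credits cross-over clearance to the initial arm. If half of the 15 PPL-clearable ESWL failures cross over and clear, at h = 40% the ESWL cleared-only rate is (10.5 + 7.5 × 0.4)/60 = 22.5%, and the gap falls from 4.4 to 1.9 points. If all 15 do, both arms have 16.5/67.5 = 24.4% and the gap is zero.

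**5. A composite in all randomised patients.** Clear and recurrence-free, at an assumed 15% recurrence after ESWL and 25% after PPL: ESWL 52.5 × 0.85/75 = 59.5%, PPL 67.5 × 0.75/75 = 67.5%. PPL leads although its assumed durability is worse.

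**The case against.** The strongest reply is that the selection argument rests on assumptions. The documents give no recurrence rate by difficulty of clearance. The only driver of recurrence they name is untreated stricture (Section 1). Section 1 also allows that heavily impacted stones in the head may still need ESWL, so the patients PPL clears need not include all those ESWL clears. Cross-over shrinks the gap and could remove it. All of this stands. A reader might infer that the endpoint is biased against PPL, or that PPL will look worse; the documents do not support that for a cleared-only comparison, and the plan does not say that only cleared patients will be compared.

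The intraductal-lithotripsy qualifier narrows the tail-stone route, since a residual stone that is never treated that way does not count. It does not close the route, because nothing separates a residual stone from a new one. The broader clearance sentence would close it, but it conflicts with the explicit definition beside it. Nothing indicates which arm tail stones would favour.

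On follow-up, Section 3 schedules everyone to 24 months, and 1:1 randomisation gives no reason for large differences between arms. A reader might infer differential follow-up by arm; the text does not show it. The problem is what the proportion means, more than its direction.

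Finally, recurrence is last of five secondary endpoints and is called an additional outcome in Section 9. That limits the weight of the point but does not answer it.

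**Conclusion.** The point holds in three parts, of different strength.

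- The mismatch between clearance and recurrence follows from the text alone: a tail stone never removed can count as a recurrence. How often this would happen cannot be worked out from the documents.
- The crude test leaves the result dependent on follow-up length: 5.4%, 10.6% or 20% for the same hazard, assuming constant hazard and a 20% risk at 24 months.
- The denominator is unstated, and neither choice gives a clean comparison of durability. The all-randomised count penalises the arm with more final clearance (14% against 18% at equal 20% recurrence, no cross-over). The cleared-only comparison is not protected by randomisation; its bias may be zero, and its size and direction depend on cross-over and on recurrence rates the documents do not give.

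The primary endpoint and the sample size are unaffected. The sponsor should make the change before the data are analysed.

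**What to change.** 1. Limit recurrence to main-duct stones in the head or body, the segments documented clear on the final pancreatogram. Reconcile the two clearance sentences in Section 3 on tail stones.
2. Replace the crude test with cumulative incidence from the date of confirmed clearance, censored at last follow-up, by arm among cleared patients. Label it a non-randomised comparison of clinically detected recurrence, because the protocol text schedules no imaging to look for stones during follow-up.
3. Add complete clearance without recurrence by a fixed time in all randomised patients, as a supporting analysis and not as the durability comparison. State how cross-over clearance and incomplete follow-up are counted. This also requires the 6-, 12- and 24-month statements to be reconciled.

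The cost is wording and analysis code. No visit or imaging is added, and Section 3 already provides a form for unscheduled pancreatic interventions up to final follow-up. The downside is that the composite mixes clearance with durability and can hide worse durability, as step 5 of the working shows, so it must be read beside the cumulative incidence curve.

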comparing ESWL with endoscopy was completed in 2007 prior to the use of PPL.⁹ Therefore, while PPL appears to be safe and effective in the treatment of these stones, there are no prospective studies evaluating its efficacy and given the relative efficacy of both techniques, a head-to-head randomized study is needed to determine which modality is optimal for patients with chronic pancreatitis.

Currently, treatment of these PD stones in the US is often dictated by the resources and expertise available at each center. Both ESWL and PPL are considered standard of care treatments with the European Society for Gastrointestinal Endoscopy (ESGE) recommending endoscopic therapy and/or ESWL as first-line therapy in patients with chronic pancreatitis who have a PD obstruction in the head or body of the pancreas.³ In regards to size, the ESGE also recommends ESWL for stones > 5 mm in diameter and ERCP for stones < 5 mm in diameter, but clarifies that PPL be performed when ESWL is not available or for stones that are not adequately fragmented by ESWL.³ In the US, ESWL is primarily performed by urologists for treatment of kidney stones, and the lack of familiarity with chronic pancreatitis has led to a general reservation by urologists in performing ESWL for pancreatic duct stones.¹¹ Furthermore, the difficulty in coordinating the schedules of anesthesia, urology, and gastroenterology together to perform ESWL for this disease has discouraged the use of the ESWL in the US.¹⁶

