Randomization will be performed using a 1:1 ratio. The investigator will then inform the patient which lithotripsy therapy will be subsequently performed.

5.4 *Treatment Regimens*

Per oral pancreatoscopy-guided lithotripsy

Standard ERP will be performed to cannulate the PD, perform pancreatic sphincterotomy, and stricture

dilation as necessary. A panreatoscope (Spyglass Digital System, Boston Scientific, Marlborough, MA) will then be inserted through the duodenoscope into the PD. For PPL, electrical pulses will be delivered through an aqueous medium by EHL or LL with the probe tip in contact with or 1-2mm away from the stone.

For EHL, the Nortech bipolar biliary EHL probe (1.9 Fr, 0.66 mm) will be used and lithotripsy will start at medium power and can be increased to high power (maximum of 100 Joules). In terms of frequency, the maximum frequency allowed will be 30 pulses/second. There will be no limit to the number of EHL probes used during a session of lithotripsy, but the maximum time of lithotripsy allowed will be 1 hour.

For LL, Holmium laser will be utilized with energy ranging from 1 to 10.5 Joules, a frequency of 8-14 Hz and a power from 5-25W. LL fibers will include 200, 272, and 365 μ meter fibers. Similar to EHL, a maximum of 1 hour of intraductal lithotripsy will be allowed. Both forms of intraductal lithotripsy can be performed during the same treatment session.

EHL and/or LL will be continued until stone fragments are \leq 3 mm or a maximum of 1 hour of lithotripsy.

Extracorporeal shock wave lithotripsy

Stone localization will first be performed by obtaining high-quality plain films of the pancreatic area in left and right oblique positions using a two-dimensional radiologic targeting system.

Depending on the stone localization, ESWL will then be performed with the patient in either slight left or right lateral decubitus with shock waves entering the body from the ventral side. The shockwaves will be focused first on the most downstream located stone within the main duct and then on other calculi moving from the head towards the body. If a stent has been inserted during preceding ERP then this may also serve as a guide to target main pancreatic duct stones by ESWL.

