In the United States, however, ESWL is primarily performed by urologists for the treatment of kidney stones. Few gastroenterologists have direct access to ESWL and urologists remain hesitant to use ESWL for non-kidney stones. Therefore, in the United States, standard therapy has become ERP.⁴ In ERP, pancreatography is performed by cannulating the PD and then injecting radio-opaque iodine contrast into the PD. Pancreatography allows for radiographic visualization of a stone and associated strictures; stone removal can be achieved by sweeping the PD with either a balloon or basket after performing a pancreatic sphincterotomy where the sphincter opening the PD is cut and coagulated. This is often followed by balloon or catheter dilation of any downstream pancreatic duct strictures. ERP is typically made more difficult by strictures downstream of the stones and the presence of numerous, large (>5mm in diameter) or hard stones.

In this study, per-oral pancreatoscopy-guided lithotripsy (**PPL**) will be compared with ESWL. Pancreatoscopy, the placement of a small endoscope directly into the PD, allows for direct visualization of the PD and stones. This allows for intraductal lithotripsy to be performed while directly visualizing the stones. Briefly, EHL, one version of intraductal lithotripsy, creates high-frequency shock-wave pulses which generate energy that can result in the fragmentation of stones. LL, on the other hand, involves the focusing of laser light on the surface of a stone which can induce wave-mediated stone fragmentation. Both techniques can fragment stones into smaller pieces, which can then be swept out of the PD using standard techniques such as balloon or basket sweeping.

Upon completion of the procedure, all patients will be observed in the post-anesthesia care unit for 1 hour as is the current standard of care. Following the index ERP session and sphincterotomy, extended recovery in the hospital or discharge will be planned per institutional practice. If patients exhibit symptoms such as intractable abdominal pain or severe N/V, they will be admitted for overnight observation. All patients will receive a phone call within 48 hours of discharge as is standard practice to identify any short-term AE's.

7. Subject and Study Stopping Criteria

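### The recurrence definition is tied to intraductal lithotripsy, the PPL arm's modality, and does not say whether a recurrent stone retreated with ESWL counts

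*Combined protocol and SAP*

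**What the plan says.** Section 3 defines recurrence as stones found after clearance was confirmed on the final pancreatogram, then adds a condition: "To be considered as recurring, the stone must require intraductal lithotripsy for removal".

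The protocol uses the term intraductal lithotripsy consistently. In Section 5.4, within the PPL regimen and after EHL and LL have been described, it states "Both forms of intraductal lithotripsy can be performed during the same treatment session". Section 6 refers to "EHL, one version of intraductal lithotripsy" and then describes LL beside it. ESWL is always named separately, as extracorporeal.

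The status of the outcome varies. Section 2 puts it among the major secondary endpoints ("5) PD stone recurrence rate"). Section 9 lists it as an additional outcome, with chi-squared or Fisher's exact tests for categorical comparisons at p<0.05. The synopsis omits it.

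**The concern.** An outcome that is compared between arms should be defined independently of the treatments being compared. Here the qualifying condition names one arm's modality, which leaves two readings.

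- **Literal.** A recurrent stone dealt with by ESWL did not require intraductal lithotripsy, so it is not a recurrence.
- **Severity threshold.** The condition means only that extraction without lithotripsy was not enough. An ESWL-retreated stone may then count, but no criterion says so.

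Sites could classify the same case differently. If the literal reading is used and ESWL retreatment is more common in one arm, that arm will appear to have fewer recurrences than it had.

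**Working it through.** **Does any other text settle the reading?**

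- The cross-over rule in Section 3 ("Cross-over and/or combination therapy will be allowed at the discretion of the endoscopist after treatment failure") concerns treatment failure, not recurrence after clearance.
- The blinded image review in Section 5.5 grades clearance as complete or partial; it is not described for recurrence.
- The form for non-scheduled interventions in Section 3 covers pancreatic interventions up to final follow-up "other than POP x ESWL planned visits". It does not alter the definition, and it is unclear whether retreatment of a recurrence falls inside that exception.
- No section says how recurrences are retreated. Section 1 reports that "the ESGE also recommends ESWL for stones > 5 mm in diameter", so ESWL retreatment is plausible. Section 6 says "Few gastroenterologists have direct access to ESWL" in the United States, so it may be uncommon.

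The question therefore stays open.

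**Illustration.** The protocol gives no recurrence rate and no power for this outcome, so there is no planned figure to reproduce. All inputs below are assumptions.

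- r = 20%: true recurrence needing lithotripsy, the same in both arms.
- fE, fP: share of ESWL-arm and PPL-arm recurrences retreated with ESWL.
- Patients at risk, using the Section 9 planning figures of 62 per arm with 90% and 70% cleared: 62 × 0.90 = 55.8, taken as 56 (PPL); 62 × 0.70 = 43.4, taken as 43 (ESWL). This is before any clearances after cross-over.

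On the literal reading, the counted rate in an arm is r × (1 − f), and the gap (PPL minus ESWL) is r × (fE − fP). On the severity reading, the counted rate is r in both arms and the gap is zero. The chance of a false p<0.05 is the summed probability, over all pairs of binomial counts, of those pairs whose two-sided p is below 0.05.

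| Reading | fE | fP | Counted ESWL | Counted PPL | False p<0.05, Fisher | False p<0.05, chi-squared (uncorrected) |
|---|---|---|---|---|---|---|
| Severity | any | any | 20% | 20% | 3.7% | 4.9% |
| Literal | 10% | 0% | 20% × 0.90 = 18% | 20% | about 4% | 5.7% |
| Literal | 25% | 0% | 20% × 0.75 = 15% | 20% | 6.8% | 10.0% |
| Literal | 50% | 0% | 20% × 0.50 = 10% | 20% | 20.5% | 28.5% |
| Literal | 50% | 25% | 10% | 15% | 7.2% | 11.6% |

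Two further literal cases show that the direction is not fixed. With 50% in both arms, the counted rates are 10% and 10%: no arm bias, but both rates are half the true value. With 0% in the ESWL arm and 25% in the PPL arm, they are 20% and 15%, so the bias runs the other way.

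**The case against.** The strongest defence is that the condition speaks of need, not of treatment received. On that view it is a deliberate threshold that leaves out small stones removable by balloon or basket, and it applies equally to both arms. This is a sensible intent and may well be what was meant. What remains is that the threshold is worded in one modality's terms and that nothing tells a site how to classify a stone retreated with ESWL.

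A second objection is that ESWL retreatment may be rare, given the access problems described in Sections 1 and 6. This also has force: at a 10% share in the ESWL arm and none in the PPL arm, the false-positive chance is close to its value without any bias. Against it, sites randomising to ESWL can presumably obtain it, so the share cannot be taken as zero.

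Third, the 43 ESWL patients at risk exclude those cleared after cross-over, whom Section 3 attributes to the initial therapy under intention to treat. Up to 62 − 43 = 19 patients could be added. Having failed ESWL, they seem less likely to be retreated with it, which would lower the ESWL-arm share. The illustration is therefore only indicative.

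A reader might infer that the definition makes ESWL look more durable than PPL. The documents do not support that. It needs both the literal reading and more ESWL retreatment in the ESWL arm, and neither is established.

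**Conclusion.** The definition is ambiguous on a point that matters for a between-arm comparison, and no other section resolves it. On the literal reading, recurrence is understated in any arm where ESWL is used for retreatment, and the comparison is biased only if that use differs by arm. On the severity reading, applied to every case, there is neither undercount nor bias. The size and direction of any bias are unknown; the figures above rest wholly on assumed recurrence, retreatment shares and numbers at risk, and the 50% versus 0% split should not be read as the expected case.

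The point is minor. The primary endpoint and the sample size are unaffected. The recurrence comparison is exploratory in any event: it is unpowered, it concerns only patients with confirmed clearance, and Section 3 schedules no follow-up imaging.

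**What to change.** In Section 3, replace the reference to intraductal lithotripsy with lithotripsy of any kind (intraductal or ESWL). Keep the word require, and state that it means extraction without lithotripsy was not sufficient. Apply the rule identically in both arms and report the retreatment modality separately. Add one line saying that events are identified from both the study procedure forms and the non-scheduled interventions form.

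Do not widen the rule to every stone on which lithotripsy happened to be performed. That would replace need with operator choice, in a trial where operators know the assigned arm, and would count stones that could have been removed without lithotripsy.

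The cost is one amended definition and one line on data sources. Stated recurrence rates may rise; in the literal 50% versus 0% scenario, the ESWL-arm rate would go from 10% to 20%. Any recurrences already classified must be re-checked; the protocol does not say whether there are any. The change affects outcome counting only, not patient management, and it does not remove the limits that keep the comparison exploratory.
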